2.1 Primary Endpoints

- Safety parameters (i.e., changes in clinical signs and symptoms from ophthalmic exam, and AEs)

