9.4 Criteria for Evaluation

9.4.1 Safety Analysis Variables

Safety and tolerability of PP-001 as measured by treatment-emergent AEs (TEAEs) and vital signs.

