9.6 Safety Analysis

Safety will be evaluated in the Safety Analysis Set by presenting summaries of AEs and vital signs.

Summary tables will be provided for all TEAEs. A treatment-emergent AE is defined as an AE with a start date and time on or after the first dose of study drug. Adverse events will be coded using the Medical Dictionary for Regulatory Activities (MedDRA®). The number and percentage of patients with TEAEs will be tabulated by system organ class and MedDRA Preferred Term for each treatment group and by severity and relationship to treatment.

Adverse events leading to premature discontinuation from the study drug and serious TEAEs will be presented either in a table or a listing.

Descriptive statistics of vital signs and the change from baseline for each scheduled evaluation will be summarized at each study visit and the worst overall post-baseline value will be provided. The number and percent of patients with treatment-emergent values with potential clinical significance will be tabulated.

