3.5 Efficacy endpoints

3.5.1 Primary endpoint

In this study to assess the safety and tolerability of ascending doses of PP-001, safety parameters (i.e., changes in clinical signs and symptoms from ophthalmic exam, and AEs), are the primary endpoints. Detailed ophthalmic examination will be used to determine efficacy and as a safety measure.

The primary efficacy variable is the best corrected visual acuity (ETDRS) change from baseline at day 14 and day 28.

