3.6 Safety endpoints

The safety endpoints are the following:

- Adverse Events (AEs);
- Vital Signs (blood pressure, heart rate);
- Electrocardiogram (ECG);
- Laboratory parameters (hematology, biochemistry and urinalysis).

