4.1 General

Descriptive statistics will be provided for all variables in the summary tables by cohorts (PP-001 0.3 µg, 0.6 µg and 1.2 µg) according to the type of variable summarized.

Quantitative variables will be summarised by using n, arithmetic mean, SD, median and range (minimum and maximum).

Categorical variables will be summarised by using frequency distributions and percentages.

| Forms | | | |
|--------------|--|------------------------------------|----------------|
| Title | | Statistical Analysis Plan Template | |
| Code | | Version | Effective Date |
| FRM_ST03_032 | | 01 | 23 Apr 2015 |
| | | 12 of 31 | |

Analysis will be performed on the treated eye only assuming that a patient is treated on one eye only.

The baseline used in the analysis for each variable is reported in the table below:

| Endpoint | Baseline |
|------------------------------------|----------------------------------|
| Electroretinography | Baseline (Day -7 up to dosing) |
| Fluorescein angiogram | Screening (Day -14 up to dosing) |
| Optical coherence tomography | Baseline (Day -7 up to dosing) |
| ETDRS | Baseline (Day -7 up to dosing) |
| Visual field | Baseline (Day -7 up to dosing) |
| Visually evoked cortical potential | Screening (Day -14 up to dosing) |
| Intraocular pressure | Baseline (Day -7 up to dosing) |
| Slit lamp examination | Baseline (Day -7 up to dosing) |
| Dilated fundoscopy | Baseline (Day -7 up to dosing) |
| Corneal endothelial microscopy | Baseline (Day -7 up to dosing) |
| Fundus photography | Baseline (Day -7 up to dosing) |
| Amsler grid | Baseline (Day -7 up to dosing) |
| Patient-reported outcomes | Baseline (Day -7 up to dosing) |
| Vital signs | Baseline (Day -7 up to dosing) |
| Laboratory assessments | Screening (Day -14 up to dosing) |

All endpoints data collected in the eCRF will be presented in the listings. PK endpoints will be listed as well.

No multiplicity adjustment will be implemented.

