7.2 Analysis of secondary efficacy endpoints

Definitions and data conventions

The following detailed ophthalmic examination will be used to determine efficacy:

Vitreous haze

- as graded by the ophthalmologist during Slit Lamp examination (classified according to Standardization of Uveitis Nomenclature Working Group)

Electroretinography

- Investigator's assessment

| Forms | | | | |
|--------------|--|------------------------------------|----------------|----------|
| Title | | Statistical Analysis Plan Template | | |
| Code | | Version | Effective Date | Page |
| FRM_ST03_032 | | 01 | 23 Apr 2015 | 18 of 31 |

Fluorescein Angiogram

- Investigator's assessment
- Hypofluorescence
- Hyperfluorescence

Optical Coherence Tomography

- Retinal thickness
- Cystoid spaces
- Subretinal Fluid
- Vitreoretinal interface abnormalities

Visual Field Measurement

- Mean deviation
- Pattern standard deviation
- Short-term fluctuation
- Corrected pattern standard deviation
- Investigator's assessment

Visually Evoked Cortical Potential

- Investigator's assessment

Intraocular Pressure

- mmHg
- Investigator's assessment

Slit Lamp Examination

- Lid
- Conjunctiva
- Cornea
- Anterior chamber
- Iris
- Lens
- Macula
- Optic nerve
- Vitreous haze

Dilated Fundoscopy

- Retinal Oedema
- Infiltration
- Vasculitis
- Retinal Ischemia
- Epiretinal Gliosis
- Vascular occlusion
- Hyperpigmentation
- Hypopigmentation
- Choroid Atrophy

Corneal endothelial microscopy

- Average cell area
- Cell density
- Investigator's assessment

| Forms | | | | |
|-------|--------------|------------------------------------|----------------|----------|
| Title | | Statistical Analysis Plan Template | | |
| Code | | Version | Effective Date | Page |
| | FRM_ST03_032 | 01 | 23 Apr 2015 | 19 of 31 |

Fundus photography

- Investigator's assessment

Amsler grid

- Investigator's assessment

Statistical analysis

Descriptive statistics will be presented by visit and for each cohort on the Safety set.

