8.2 Clinical laboratory evaluation

Statistical analysis

Hematology, biochemistry parameters and their change from screening will be summarised by cohort at each available visit by means of descriptive statistics.

Shift tables presenting the number and the percentage of patients in each bivariate category (screening visit versus Visit 9) with regards to Investigator’s interpretation (Normal, NCS, CS) will be presented by cohort for all laboratory parameters.

Urinalysis parameters will be listed only.

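### Change on eye examination is part of the primary safety endpoint, but for 11 of 12 eye examinations the SAP text plans no change, shift or new-or-worsened summary

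*SAP*

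**What the plan says.** **Endpoint.** Protocol 2.1 defines the primary endpoint as "Safety parameters (i.e., changes in clinical signs and symptoms from ophthalmic exam, and AEs". SAP 3.5.1 repeats it: "safety parameters (i.e., changes in clinical signs and symptoms from ophthalmic exam, and AEs), are the primary endpoints". The same SAP section says the eye examination serves both efficacy and safety.

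**Safety analysis.** Protocol 9.4.1 narrows the safety variables: "Safety and tolerability of PP-001 as measured by treatment-emergent AEs (TEAEs) and vital signs". Protocol 9.6 does likewise: "Safety will be evaluated in the Safety Analysis Set by presenting summaries of AEs and vital signs". SAP 3.6, which opens with "The safety endpoints are the following", lists adverse events, vital signs, ECG and laboratory parameters. SAP section 8 adds physical examination, and 8.6 foresees nothing further.

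**Eye examinations.** SAP 7.1 summarises visual acuity with change from baseline. SAP 7.2 lists the items of the other 11 examinations and closes with "Descriptive statistics will be presented by visit and for each cohort on the Safety set".

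**Baselines.** SAP 4.1 says "The baseline used in the analysis for each variable is reported in the table below" and lists 15 endpoints, among them all 12 eye examinations.

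**Contrast.** For laboratory parameters SAP 8.2 plans change from screening and "Shift tables presenting the number and the percentage of patients in each bivariate category". Vital signs (8.3) and patient-reported outcomes (7.3) also get a change from baseline.

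**The concern.** The endpoint is worded as change, while the method given for most of the examinations describes each visit separately. The two differ when signs can already be present before dosing, and here they can: study eyes have chronic uveitis. If a sign clears in one patient and appears in another, the count in the cohort stays the same and the table shows nothing.

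Adverse event reporting is a partial back-up. Protocol section 7 requires new or worsened occurrences to be reported. It also keeps abnormal assessments associated with the disease out of adverse event reporting unless the investigator judges them more severe than expected. Signs that resemble uveitis, such as retinal oedema or vasculitis, are where that filter applies.

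At stake is whether the report of a first-in-human intravitreal study contains a prespecified summary of the examination half of its primary endpoint.

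**Working it through.** There is no sample-size or power figure to reproduce; the study is descriptive (SAP 3.3, 4.1).

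**1. Examinations.** The visit schedule lists 12: electroretinography, fluorescein angiogram, OCT, visual acuity, visual field, visually evoked potential, intraocular pressure, slit lamp, dilated fundoscopy, corneal endothelial microscopy, fundus photography and Amsler grid. Only visual acuity has a stated change analysis: 12 − 1 = 11 without.

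**2. Items in SAP 7.2** (vitreous haze counted once, under slit lamp):

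| Examination | Items |
|---|---|
| Electroretinography | 1 |
| Fluorescein angiogram | 3 |
| OCT | 4 |
| Visual field | 5 |
| Visually evoked potential | 1 |
| Intraocular pressure | 2 |
| Slit lamp | 9 |
| Fundoscopy | 9 |
| Corneal microscopy | 3 |
| Fundus photography | 1 |
| Amsler grid | 1 |
| Total | 39 |

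In the SAP text, 0 of 39 has a change, shift or new-since-baseline summary.

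**3. Baselines in SAP 4.1.** Of 15 endpoints, four have an analysis that uses the baseline: visual acuity (7.1), patient-reported outcomes (7.3), laboratory (8.2) and vital signs (8.3). 15 − 4 = 11, and all 11 are eye examinations.

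**4. Table titles in SAP 9.3.** The visual acuity, patient-reported outcome, vital signs and laboratory titles mention change or shifts. Tables 14.2.3.1, 14.2.4.1 and 14.2.5.1, which carry the 11 examinations, do not.

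**5. What counts by visit leave open.** Take a present/absent sign in a cohort of n = 4 (SAP 3.1), complete data, b patients affected at baseline and v at a later visit. The number of new cases lies between max(0, v − b) and min(v, n − b).

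- b = 1, v = 1: max(0, 0) = 0 to min(1, 3) = 1.
- b = 2, v = 2: max(0, 0) = 0 to min(2, 2) = 2.
- b = 2, v = 3: max(0, 1) = 1 to min(3, 2) = 2.

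The bounds differ whenever b and v both lie between 1 and 3, which is 3 × 3 = 9 of the 5 × 5 = 25 possible pairs. This is a count of cases and says nothing about how often they occur.

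**6. How often it might matter (assumed rates; the documents give none).** Suppose the sign is present at baseline in 25–75% of eyes, resolves in 10–50% of those and appears in 10–25% of the rest, with patients independent. Per patient, P(new) = (1 − presence) × onset and P(resolved) = presence × resolution. Masking means at least one new case and no rise in the count.

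| Presence, resolution, onset | P(≥1 new) | P(masked) | P(masked given ≥1 new) |
|---|---|---|---|
| 0.25, 0.10, 0.25 | 0.564 | 0.036 | 0.064 |
| 0.50, 0.25, 0.25 | 0.414 | 0.125 | 0.303 |
| 0.50, 0.25, 0.10 | 0.186 | 0.059 | 0.320 |
| 0.75, 0.50, 0.10 | 0.096 | 0.072 | 0.744 |

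Over the whole range, the unconditional probability per sign, cohort and visit runs from about 2% (0.25, 0.10, 0.10) to about 22% (0.50, 0.50, 0.25).

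**7. Numeric items.** By their names, eight of the 39 are numeric: retinal thickness, four visual-field indices, pressure in mmHg, cell area and cell density. With complete data their mean change equals the difference of the by-visit means, so step 5 does not apply. The largest individual change still cannot be recovered, and SAP 4.7 does not impute, so missing values break the equality.

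**The case against.** **Section 8 is not empty of eye safety.** A reader might infer that the SAP has no ophthalmic safety analysis. The documents do not support that. SAP 8.1 tabulates treatment-emergent events, serious events and drug reactions by organ class and term, which includes ocular events, and those are half of the endpoint. The examination tables also use the Safety set, so placing them under efficacy is partly a matter of labelling. What stands is that no examination-based change summary is stated in either section.

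**Comparison with baseline may have been intended.** SAP 4.1 defines the baselines, SAP 9.2 has a general listing rule for change from baseline, and Protocol 9.8 relates change from baseline in efficacy endpoints to exposure. The table shells are in a separate appendix that was not available. A reader might conclude from the table titles that the columns are absent, but titles are weak evidence. The point therefore concerns the SAP text only.

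**Four patients can be read by eye.** Listings 16.2.6.1 to 16.2.6.4 show each patient, and Protocol 10.2 has the safety board follow the examinations. A reader might infer that worsening would go unnoticed during the trial; the documents point the other way. Reading listings is nevertheless not a prespecified summary of a primary endpoint.

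**Rabbit toxicity.** SAP 7.2 does not name the findings in Protocol 1.3.3 (detachment, tear, exudation, choroidal changes, floaters). It would go too far to say they would be missed: OCT, angiogram, fundoscopy or adverse event terms can pick up some of them. The human equivalent of the rabbit no-adverse-effect dose is 10 × 4 / 1.5 = 26.7 µg, about 22 times the 1.2 µg dose (26.7 / 1.2 = 22.2).

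**The masking rates are assumed.** This is correct. The highest conditional figure, 0.744, conditions on an event of probability 0.096. The argument does not need these rates; step 5 is enough.

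**Conclusion.** The point holds for the text of the SAP. Apart from visual acuity and ocular adverse events, the examination half of the primary safety endpoint has no stated summary of change: 11 of 12 examinations, 39 items and 11 defined but unused baselines. For categorical signs the planned counts by visit cannot give the number of patients who worsened; 2 of 4 followed by 2 of 4 leaves 0 to 50% of the cohort as possible new cases. For numeric items the loss is smaller.

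The consequence is limited to the planned summary of the primary endpoint. It does not reach patient protection, and no inferential result depends on it. The conclusion assumes that the unseen shells do not already contain these columns. If they do, a sentence in the SAP pointing to them closes the point. The change is worth making because it is cheap and the endpoint is primary.

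**What to change.** In SAP 7.2, cross-referenced from section 8 as the ophthalmic safety summary, add the following for all 11 examinations in the treated eye, by cohort and scheduled post-baseline visit, against the SAP 4.1 baseline:

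- **Categorical or graded items and investigator assessments:** a shift table, or the number of patients with a finding new or worsened since baseline (absent then and present now, or a higher grade than at baseline).
- **Numeric items** (intraocular pressure, retinal thickness, visual-field indices, endothelial cell area and density): change from baseline, including minimum and maximum.

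The SAP does not give the field type of every item, so each should be assigned to one of the two groups when the tables are specified. Separate rows for adverse event terms are unnecessary, since Table 14.3.1.2 already covers them.

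**Cost:** one or two more tables and their programming, from existing data and with no new examination. With four patients per cohort many cells will be zero, and there is some overlap with Tables 14.2.3.1 to 14.2.5.1.

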7.3 Analysis of other efficacy endpoints

Definitions and data conventions

National Eye Institute Visual Functioning Questionnaire 25 (VFQ-25)

Visual functioning is assessed using the 25-item NEI-VFQ. The questionnaire contains 25 vision-targeted questions (grouped into 11 subscales) plus one single-item question related to general health (Question 1). The responses to the 25 vision-related questions are used to generate 12 subscale scores, and 11 of them are then averaged to produce an overall composite score to be used for analysis. Averaging the subscale scores gives equal weight to each subscale, whereas averaging the scores of the individual questions would give more weight to the subscales containing more questions.

The three-step process for deriving the overall NEI-VFQ composite score is explained in the VFQ-25 Manual “The National Eye Institute 25-Item Visual Function Questionnaire (VFQ-25)” (Version 2000), and the details of the algorithm are given below.

Step 1

The categorical responses to the survey are assigned numeric values as dictated by the design of the questionnaire, which is available online from the National Eye Institute (2000).

The numeric values are then re-coded to a scale between 0 and 100; such that a higher score represents better eye functioning. The re-coding rules are given in the table below.

| Question Numbers | Original Response Category ^(a) | Re-coded Value |
|---------------------------------------|---|----------------------------|
| 1 | 1 2 3 3.5 4 | 0 25 50 75 100 |
| 3, 4, 15c ^(b) , 17, 18, 19 | 1 2 3 4 5 | 100 75 50 25 0 |
| 2 | 1 2 3 4 | 0 20 40 60 |

| Forms | | | |
|--------------|--|------------------------------------|----------------|
| Title | | Statistical Analysis Plan Template | |
| Code | | Version | Effective Date |
| FRM_ST03_032 | | 01 | 23 Apr 2015 |
| | | 20 of 31 | |

| Question Numbers | Original Response Category ^(a) | Re-coded Value |
|--|---|----------------|
| 5, 6, 7, 8, 9, 10, 11, 12, 13, 14, 16, 16a | 5 | 80 |
| | 6 | 100 |
| | 1 | 100 |
| | 2 | 75 |
| | 3 | 50 |
| | 4 | 25 |
| 20, 21, 22, 23, 24, 25 | 5 | 0 |
| | 6 | * |
| | 1 | 0 |
| | 2 | 25 |
| | 3 | 50 |
| | 3.5 | 75 |
| | 4 | 100 |

(a) Pre-coded response choices as printed in the questionnaire.

(b) Question 15c has 4 responses levels (1 to 4), but is expanded to 5 levels using Question 15b:

If 15b = 1, then 15c should be recoded to 0.

If 15b = 2, then 15c should be recoded to missing.

If 15b = 3, then 15c should be recoded to missing.

* Response choice 6 indicates that the person does not perform the activity because of non-vision related problems.
If this choice is selected, the item is coded as missing.

Step 2

The re-coded scores are grouped into 12 categories as shown in the table below, and the mean of the non-missing values in each category represents the subscale score for that category.

| Scale | Number of Questions | Question Numbers to be Averaged for Subscale Score (after re-coding) |
|---------------------|---------------------|--|
| General Health | 1 | 1 |
| General Vision | 1 | 2 |
| Ocular Pain | 2 | 4, 19 |
| Near Activities | 3 | 5, 6, 7 |
| Distance Activities | 3 | 8, 9, 14 |
| Vision-Specific: | | |
| Social Functioning | 2 | 11, 13 |
| Mental Health | 4 | 3, 21, 22, 25 |
| Role Difficulties | 2 | 17, 18 |
| Dependency | 3 | 20, 23, 24 |
| Driving | 3 | 15c, 16, 16a |
| Color Vision | 1 | 12 |
| Peripheral Vision | 1 | 10 |

Step 3

The overall composite score is calculated as the mean of 11 subscale scores that were derived in Step 2, excluding the “General Health” subscale score. If not all subscale scores are calculated due to missing values, the mean of the available subscale scores will be taken.

SF36™ Health Survey Version 2 (SF-36v2)

|  cros nt | | Forms | | | |
|--|--|------------------------------------|---------|----------------|----------|
| | | Statistical Analysis Plan Template | | | |
| | | Code | Version | Effective Date | Page |
| | | FRM_ST03_032 | 01 | 23 Apr 2015 | 21 of 31 |

The SF-36 is a multi-purpose, short-form health survey with only 36 questions yielding 8 health domain scales and 2 psychometrically based physical and mental component summary measures. The standard form of the SF-36v2 will be used. The question number 2 will not be used to score any of the 8 health domain scales or 2 summary measures because it is not applicable.

The 8 health domain scales are referred to as the ‘Physical Functioning (PF)’, ‘Role- Physical (RP)’, ‘Bodily Pain (BP)’, ‘General Health (GH)’, ‘Vitality (VT)’, ‘Social Functioning (SF)’, ‘Role-Emotional (RE)’, and ‘Mental Health (MH)’ scales. The 2 summary measures are referred to as the physical component score (PCS) and mental component score (MCS).

The methods of SF-36v2 scoring, handling of missing values, z- and T-score transformations are provided below.

Each item on the 36-item short-form health survey will be answered by the patients (on scales of 1 to 3, 1 to 5, or 1 to 6). Some of those answers will then be re-coded so that across all questions, a higher score will indicate a better health state. Questions 3a-3j, ,9a, 9d, 9e, 9h, 11b, 11d will be scored as recorded; the other questions will have the scores transformed as shown in the

Table 1.

The raw score for the following 8 scales will be calculated by summing the scores (either original or re-coded depending on the question) for the set of questions listed in **Table 2** if all of the questions within that scale are answered. If < 50% of the questions within a scale is answered, then the raw score will not be calculated.

Table 1

| SF-36v2: Re-code | | | | | | |
|---|------------------------------------|-----|-----|-----|-----|-----|
| Question | Original code and re-code response | | | | | |
| Question number: 1 | | | | | | |
| Original response | 5 | 4 | 3 | 2 | 1 | |
| Re-coded response | 5 | 4.4 | 3.4 | 2 | 1 | |
| Questions numbers: 6 | | | | | | |
| Original response | 1 | 2 | 3 | 4 | 5 | |
| Re-coded response | 5 | 4 | 3 | 2 | 1 | |
| Questions numbers: 4a-4d, 5a-5c, 9b, 9c, 9f, 9g, 9i, 10, 11a, 11c | | | | | | |
| Original response | 5 | 4 | 3 | 2 | 1 | |
| Re-coded response | 1 | 2 | 3 | 4 | 5 | |
| Question number: 7 | | | | | | |
| Original response | 1 | 2 | 3 | 4 | 5 | 6 |
| Re-coded response | 6 | 5.4 | 4.2 | 3.1 | 2.2 | 1 |
| Question number: 8 (if question number 7 is answered) | | | | | | |
| Original response to #8 | 1 | 1 | 2 | 3 | 4 | 5 |
| Original response to #7 | 1 | 2-6 | 1-6 | 1-6 | 1-6 | 1-6 |
| Re-coded response | 6 | 5 | 4 | 3 | 2 | 1 |

|  cros nt | Forms | | | |
|---|--------------|------------------------------------|----------------|----------|
| | Title | Statistical Analysis Plan Template | | |
| | Code | Version | Effective Date | Page |
| | FRM_ST03_032 | 01 | 23 Apr 2015 | 22 of 31 |

| SF-36v2: Re-code | | | | | | |
|---|------------------------------------|------|-----|------|---|--|
| Question | Original code and re-code response | | | | | |
| Question number: 8 (if question number 7 is NOT answered) | | | | | | |
| Original response | 1 | 2 | 3 | 4 | 5 | |
| Re-coded response | 6 | 4.75 | 3.5 | 2.25 | 1 | |

Table 2

| SF-36v2: Scales | |
|---------------------------|--------------------|
| Scales | Questions |
| Physical functioning (PF) | 3a to 3j |
| Role – physical (RP) | 4a to 4d |
| Bodily pain (BP) | 7, 8 |
| General health (GH) | 1, 11a to 11d |
| Vitality (VT) | 9a, 9e, 9g, 9i |
| Social functioning (SF) | 6, 10 |
| Role - emotional (RE) | 5a to 5c |
| Mental health (MH) | 9b, 9c, 9d, 9f, 9h |

If $\geq 50\%$ but not all of the questions are answered on a domain, first the non-missing questions are recoded (if necessary) and then summed. An average score is calculated for those non-missing scores and that average score is filled in as the score to be used for the value of the missing questions. The raw score is then calculated as the sum of all the question scores. For example, for the VT scale, if questions 9a, 9e, and 9g are answered but question 9i is missing, the algorithm will proceed as shown in **Table 3** from left to right:

Table 3

| SF-36v2: Algorithm for unanswered questions | | | | | |
|---|---------------------------|--------------------------|--|--|--|
| Question | Patient recorded response | Response after re-coding | | Average is filled in for missing responses | |
| 9a | 1 | 5 | Average of non-missing scores = $(5+3+5)/3 = 4.33333$. | 5 | Raw score = $5+3+5+4.3333... = 17.33333...$ |
| 9e | 3 | 3 | | 3 | |
| 9g | 5 | 5 | | 5 | |
| 9i | Missing | Missing | | 4.33333... | |

After the raw score is calculated, the raw score is then converted into a transformed scale score (on a scale of 0 to 100) using the following transformation:

| Forms | | | | |
|--------------|--|------------------------------------|----------------|----------|
| Title | | Statistical Analysis Plan Template | | |
| Code | | Version | Effective Date | Page |
| FRM_ST03_032 | | 01 | 23 Apr 2015 | 23 of 31 |

$$\text{Transformed scale score} = \frac{\text{Total raw score} - \text{Lowest possible raw score}}{\text{Possible raw score range}} \times 100$$

The transformed scale scores will then be standardised using the following formula for the z-score transformation:

$$z\text{-score} = \frac{\text{Transformed scale score} - \text{Mean of General US population}}{\text{Standard deviation of General US population}}$$

For example, a VT total raw score of 17.33333 would be transformed as follows:

$$\text{VT transformed scale score} = \frac{17.33333 - 4}{16} \times 100 = 83.3333125$$

As shown in Table 4, the lowest possible VT score equals 4 and the possible VT total raw score range equals 16. This transformation converts the lowest and highest possible raw scores to 0 and 100, respectively. Scores between these values represent the percentage of the total possible score achieved.

When based on the 1998 US general population, the VT z-score is as follows:

$$\text{VT z-score} = \frac{83.3333125 - 58.41968}{20.87823}$$

The lowest possible raw score, possible raw score range, mean and standard deviation for each scale are shown in **Table 4**.

Table 4

| Lowest possible raw score and range, and means and standard deviations for deriving the z-scores for the scales of the SF-36v2 ACUTE form | | | | |
|---|---------------------------|--------------------------|----------|--------------------|
| Scale | Lowest possible raw score | Possible raw score range | Mean | Standard deviation |
| PF | 10 | 20 | 82.62455 | 24.43176 |
| RP | 4 | 16 | 82.65109 | 26.19282 |
| BP | 2 | 10 | 73.86999 | 24.00884 |
| GH | 5 | 20 | 70.78372 | 21.28902 |
| VT | 4 | 16 | 58.41968 | 20.87823 |
| SF | 2 | 8 | 85.11568 | 23.24464 |
| RE | 3 | 12 | 87.50009 | 22.01216 |
| MH | 5 | 20 | 75.76034 | 18.04746 |

| Forms | | | |
|--------------|--|------------------------------------|----------------|
| Title | | Statistical Analysis Plan Template | |
| Code | | Version | Effective Date |
| FRM_ST03_032 | | 01 | 23 Apr 2015 |
| | | | 24 of 31 |

The physical and mental component raw scores are composed of a combination of the 8 domain z-scores and these will be calculated based on each domain scale z-score multiplied by a constant provided in **Table 5**, and then add the 8 scales together.

To illustrate, a portion of the formula for aggregating scales when estimating an aggregate physical and mental component score are as follows:

$$\text{Aggregate PCS} = (\text{PF z-score} \times 0.42402) + \dots + (\text{GH z-score} \times -0.22069)$$

$$\text{Aggregate MCS} = (\text{PF z-score} \times -0.22999) + \dots + (\text{MH z-score} \times 0.48581)$$

Note: if any of the 8 domain z-score is missing the aggregate PCS and MCS will be missing.

The T-scores for the 8 scale scores will be calculated by multiplying the scale z-scores by 10 and adding 50.

To illustrate, a portion of the formula for transforming domain scale z-scores to T-scores:

$$\text{PF T-score} = 50 + (\text{PF z-score} \times 10)$$

$$\text{MH T-score} = 50 + (\text{MH z-score} \times 10)$$

The physical and mental component T-scores will then be calculated by multiplying the component raw scores by 10 and adding 50.

The formulas for computing the norm-based T-score for each component summary measure are:

$$\text{PCS T-score} = 50 + (\text{Aggregate physical component score} \times 10)$$

$$\text{MCS T-score} = 50 + (\text{Aggregate mental component score} \times 10)$$

Table 5

| SF-36v2: Scale constants used to calculate component scores | | |
|---|---------------------------|-------------------------|
| Scale | Physical health component | Mental health component |
| PF | 0.42402 | -0.22999 |
| RP | 0.35119 | -0.12329 |
| BP | 0.31754 | -0.09731 |
| GH | 0.24954 | -0.01571 |
| VT | 0.02877 | 0.23534 |
| SF | -0.00753 | 0.26876 |
| RE | -0.19206 | 0.43407 |
| MH | -0.22069 | 0.48581 |

The responses to the SF-36v2 at Visit 9 (Day 28) will also be categorized as improved, worsened and stable based on the changes from baseline in T-score. The criteria for a MCID (Ware et al, 2007) will be used to assign a visit response for each score (see **Table 6**). The T-scores will be based on the 1998 US general population survey as reported in Ware et al, 2007. At follow up visit, the criteria that will be used to assign a visit response to the changes from baseline will be based on the MCIDs shown in **Table 6**.

Only patients with a non-missing score at both baseline and at Visit 9 (Day 28) will be considered eligible for categorization.

| Forms | | | | |
|--------------|--|------------------------------------|----------------|----------|
| Title | | Statistical Analysis Plan Template | | |
| Code | | Version | Effective Date | Page |
| FRM_ST03_032 | | 01 | 23 Apr 2015 | 25 of 31 |

Table 6

| Response Categories | | | | |
|---------------------|--------------|--------------|-----------|--|
| Visit response | | | | |
| Score | Improved | Worsened | Stable | |
| PCS | $\geq + 3.1$ | $\leq - 3.1$ | Otherwise | |
| MCS | $\geq + 3.8$ | $\leq - 3.8$ | Otherwise | |
| PF | $\geq + 3.5$ | $\leq - 3.5$ | Otherwise | |
| RP | $\geq + 3.2$ | $\leq - 3.2$ | Otherwise | |
| BP | $\geq + 4.5$ | $\leq - 4.5$ | Otherwise | |
| GH | $\geq + 5.7$ | $\leq - 5.7$ | Otherwise | |
| VT | $\geq + 5.5$ | $\leq - 5.5$ | Otherwise | |
| SF | $\geq + 5.0$ | $\leq - 5.0$ | Otherwise | |
| RE | $\geq + 3.8$ | $\leq - 3.8$ | Otherwise | |
| MH | $\geq + 5.5$ | $\leq - 5.5$ | Otherwise | |

EuroQol-5 Dimensions Health Questionnaire (EQ-5D)

The EuroQol EQ-5D-5L consists of five dimensions (mobility, self-care, usual activities, pain/discomfort, and anxiety/depression) each of which is recorded on a 5 point scale (1 to 5). The first response choice (“no problems”) is coded as a 1; the second (“slight problems”) is coded as a 2; the third (“moderate problems”) is coded as a 3; the forth (“severe problems”) is coded as a 4; the fifth (“extreme problems”) is coded as a 5 as indicated on the questionnaire. Values recorded in the eCRF will not be recoded.

Each combination of dimensions scores for a single subject is concatenated together to form the Health State (e.g. a string variable ‘11233’ for the scores in mobility=1, self-care=1, usual activities=2, pain/discomfort=3, and anxiety/depression=3).

The five dimensions will also be converted into a Health State Index on a scale of approximately 0 to 1, where scores close to 0 represent a health state of death and a score of 1 represents full quality of life. The conversion between the ordinal scores to an index will be carried out using UK weighting and using SAS programs supplied by EUROQOL.

A higher score indicates a more preferred health status. For the precision of TLFs the actual derived value will be used in all summary statistic calculations but will be listed to two decimal places. Summary statistics will be rounded based on the same decimal precisions.

The final EQ-5D question (the ‘Scored Health Today’) asks respondents to rate their present health status on a vertical 0 to 100 visual analogue scale of 20 cm, with 0 labelled as “Worst imaginable health state” and 100 labelled as “Best imaginable health state.” The scale is marked in increments of “10,” with values labelled at each decile.

| Forms | | | |
|--------------|--|------------------------------------|----------------|
| Title | | Statistical Analysis Plan Template | |
| Code | | Version | Effective Date |
| FRM_ST03_032 | | 01 | 23 Apr 2015 |
| | | | 26 of 31 |

Statistical analysis

The EuroQol-5 Questionnaire (EQ-5D-5L) Health State Index as the Scored Health, NEI-VFQ overall composite score and SF-36v2 scores as measured at baseline and Visit 9 (Day 28), will be summarised using descriptive statistics, and the change in score from the baseline visit will be calculated for each patient.

